## 10. STATISTICAL ANALYSIS

### 10.1 Primary study parameter(s)

Given the obvious advantages of preserving a patients' own knee, KJD needs to demonstrate 'non-inferiority' on the medium-long (2 year) term.

A full statistical analysis plan (SAP) will be in place prior to the analysis of trial data. All analyses and patient populations will be predefined in this SAP. Both intention-to-treat (ITT) and per protocol (PP) analyses have biases so neither can be regarded the 'gold standard' for non-inferiority trials but these approaches can make critical differences to the results of a trial (18). The trial will be analyzed and reported according to CONSORT extension for Non-Inferiority and Equivalence Randomized Trials (19).

The primary endpoint, the total WOMAC score at 2 years, will be compared between groups using (multivariable) random effects (mixed) modelling to account for the nested and longitudinal structure of the data over the 24 months follow-up. In case residuals of the model are not normally distributed, transformed scores will be used in the regression modelling. In this analysis time will be used as a categorical variable (5, 8, 12 and 24 months), and an interaction between time and the treatment-arm variable will also be included. A random intercept at patient level as well as at center level will be included. The stratification factors for randomization, center (using a random intercept) and gender, as well as a limited number of a priori defined prognostic factors (i.e. baseline WOMAC total score, age, BMI, and severity of cartilage damage) will be accounted for in this analysis used as fixed covariates. Baseline WOMAC score will be used as a continuous covariate (similar to the outcome variable), as well as age and severity of cartilage damage which can be regarded a reasonable assumption given the limited, expected range (in patients with age  $\leq 65$  and severe knee OA (K&L grade  $> 2$ )). As we expect that the effect of BMI may be non-linear, we will use BMI as a categorical variable using the CDC classification (BMI  $< 18.5$ , underweight;  $18.5$  to  $<25$ , healthy weight; BMI  $25.0$  to  $<30$ , overweight; BMI  $30.0$  to  $< 35$  (max allowed in the study) obesity).

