A random effect of time will also be tested in the model. The difference in mean total WOMAC score at 24 months between treatment groups will be estimated from this model with a 95% confidence interval (CI). The lower limit of this interval will be compared to the non-inferiority limit. If the lower limit of the confidence interval does not overlap the non-inferiority limit, KJD will be considered non-inferior. The non-inferiority limit is predefined

and accepted as 15 for the primary outcome (WOMAC total score) (See also at sample size calculation, 14).

The above analysis will be performed primarily on the per protocol (PP) population, i.e. patients that received their randomised treatment (and completed the 6 week distraction period for patients randomised to KJD only). The analysis will be repeated, for sensitivity reasons, for the ITT population defined as all patients who were randomized to one of the treatments.

A secondary analysis of the primary endpoint will be performed using (simple, multivariable) linear regression modelling, using only the 24 month WOMAC total scores. Multiple imputation will be used with > 10% missing data. This analysis will also be made the primary analysis when assumptions for the mixed model analysis do not seem to hold or convergence problems occur.

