## **10.2 Secondary study parameter(s)**

The analysis for continuous secondary outcomes follow the analysis strategy of the primary outcome. Binary, secondary outcomes will be compared using logistic multi-level regression analysis. The stratification factors for randomization (center and gender) will be used as (fixed) covariates in the analysis and the analysis will be adjusted by a limited number of a priori defined prognostic factors (e.g. baseline WOMAC total score, age, BMI, and severity of joint damage). Relative Risks (RR) with 95% confidence intervals will be estimated.

The upper limit (lower limit for response outcomes) of the confidence interval will be compared to the respective pre-defined non-inferiority limits to determine 'non-inferiority'. An ITT and a PP analysis will be performed.

The number of complications will be reported as the frequency and percentage of events and frequency and percentage of patients experiencing events per (type of) complication. Additional arthroplasty procedures, specifically a primary knee prosthesis after KJD and revision surgery (e.g. total after hemi prosthesis) after a primary knee prosthesis will be described per group.

Radiographic assessment of joint space width, as an indicator of cartilage repair, over a two-year period will be reported descriptively in the KJD group. Differences from baseline (pre-treatment) will be tested with paired t-tests or Wilcoxon rank sum tests depending on the distribution of the data at 1 and 2 years follow-up.

Missing data will be minimised using centralised data acquisition for all participating centers coordinated from the UMC Utrecht with appropriate monitoring on data queries and will be imputed using multiple imputation by chained equations for the analyses.

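### The primary analysis can switch, on a loosely worded data-dependent trigger, to a 24-month-only regression whose imputation rule is incomplete and not reconciled with section 10.2

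*Protocol*

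**What the plan says.** All references are to the protocol.

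- **Default primary analysis (10.1).** WOMAC total at 2 years "will be compared between groups using (multivariable) random effects (mixed) modelling to account for the nested and longitudinal structure of the data", with time as a categorical variable (5, 8, 12 and 24 months). The 24-month contrast is compared with the margin of 15.
- **First remedy (10.1).** "In case residuals of the model are not normally distributed, transformed scores will be used in the regression modelling".
- **Secondary analysis (10.1).** A multivariable linear regression "using only the 24 month WOMAC total scores".
- **Switch rule (10.1).** "This analysis will also be made the primary analysis when assumptions for the mixed model analysis do not seem to hold"; the same sentence adds failure to converge as a second trigger.
- **Imputation for that regression (10.1).** "Multiple imputation will be used with > 10% missing data". The denominator of the 10% is not given, nor is the method at or below it.
- **Imputation in 10.2, under the heading for secondary parameters.** Missing data "will be imputed using multiple imputation by chained equations for the analyses", with no threshold.
- **Link between the sections (10.2).** "The analysis for continuous secondary outcomes follow the analysis strategy of the primary outcome".

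Section 10.1 also promises a full SAP, predefining all analyses, before trial data are analysed. Section 8.2 states that the study is unblinded.

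**The concern.** Four features of the stated rules cause difficulty.

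1. Whether assumptions appear to fail can be judged only after the model has been fitted to outcome data. The protocol names no diagnostic, threshold or decision-maker. The regression is run in any case as a secondary analysis, so both results will exist.
2. Non-normal residuals set off two rules, transformation and switch, with no order between them. A linear regression makes the same residual assumption, so switching does not repair that failure.
3. The replacement drops the 5, 8 and 12 month scores. Those scores let the mixed model allow for dropout that depends on how a patient was doing earlier.
4. The fallback is imputed only above 10% missing. At or below that level the natural reading is complete-case analysis, though this is an inference. Section 10.2 sets no threshold.

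The planning assumption puts the true difference at 12 and the margin at 15, a gap of 3 points. Biases of a fraction of a point to a point therefore matter here.

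**Working it through.** **1. The plan's own figure.** Section 4.4 gives margin 15, assumed difference 12, SD 15, one-sided 2.5% and 90% power.
n per arm = 2 × 15² × (1.960 + 1.282)² / (15 − 12)² ≈ 526 by the normal approximation. The exact t calculation first reaches 90% at 527 (90.04%; 526 gives 89.98%). The stated 527 is reproduced.
SE of the difference = 15 × √(2/527) = 0.924 points.

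**2. Would imputation be triggered at the planned loss?** Section 4.4 randomises 600 per group to retain 527, and 1 − 527/600 = 12.2%. That exceeds 10%, so at the planned level the fallback would be imputed. The gap in the rule opens only if retention is better than planned. The missing denominator also matters: with 1:1 arms, 20% missing in one arm and 0% in the other is 10% overall, which does not exceed the threshold.

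**3. Effect of choosing between two tests.** Suppose each test has one-sided 2.5% error and the statistics are bivariate normal with correlation r. The chance that at least one rejects is 3.2% at r = 0.95 and 2.8% at r = 0.99. In the simulation in step 5 the correlations were 0.96-0.99, so this range applies.

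**4. Effect of an unimputed fallback (illustration).** Assumptions not in the protocol: 10% missing in the distraction arm (KJD), those patients d = 5 to 10 points worse than completers, and uninformative missingness in the prosthesis arm (KP).
Bias towards KJD = 0.10 × d = 0.5 to 1.0 points, or 17-33% of the 3-point gap.
One-sided error at the margin = 1 − Φ(1.96 − bias/0.924):
- d = 5: 1 − Φ(1.96 − 0.541) = 7.8%
- d = 10: 1 − Φ(1.96 − 1.082) = 19.0%

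**5. Comparison with the mixed model.** Step 4 has no comparator, so the two analyses were simulated side by side. There were 600 per arm, SD 15, a true difference at the margin, equal correlation between visits, complete earlier scores, and 3,000 runs per setting. Missingness at 24 months was more likely in KJD patients with poor earlier scores and random in KP. All of these settings are assumptions.

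| Correlation between visits | Missing in KJD | Complete-case bias towards KJD | Error, complete-case | Error, mixed model |
|---|---|---|---|---|
| 0.5 | 4.7% | 0.35 | 5.5% | 2.6% |
| 0.5 | 9.2% | 0.65 | 11.2% | 2.3% |
| 0.7 | 5.0% | 0.50 | 8.1% | 2.5% |
| 0.7 | 9.6% | 0.92 | 17.1% | 2.4% |

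With missingness completely at random in both arms, each analysis held about 2.5%, and taking the better of the two gave 2.6-3.1%.

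**6. The two imputation rules side by side.** The 10.1 rule has a threshold and is attached to one regression of the primary endpoint. The 10.2 rule has none, and only its closing reference to the analyses could extend it to the primary endpoint. For continuous secondary outcomes both apply: 10.2 imposes its own rule and also adopts the 10.1 strategy.

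**The case against.** The strongest defence is that this is a named fallback, not an open menu. The protocol designates one alternative in advance and plans to report it anyway. It promises a SAP before any analysis, and diagnostics and decision rules may be set there. Non-convergence is a reasonably objective trigger, and a single-time-point regression is a legitimate method. An unblinded trial does not mean that model checks are made with the treatment contrast in view. All of this stands.

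Three stronger readings are tempting, and the protocol does not support them.

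- **That the primary result is left to a post-hoc choice.** A reader might infer this from the trigger wording. The promised SAP and the single named alternative argue against it, and step 3 shows that the choice alone costs well under one percentage point.
- **That the fallback is complete-case up to 10% missing.** The protocol does not say so. It is silent on the method at or below 10%.
- **That 10.1 and 10.2 flatly contradict each other on the primary endpoint.** The 10.2 sentence stands under secondary parameters. It can be read as naming the method, with the 10% as a trigger for one regression.

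The error figures are also open to challenge. They need informative loss in one arm, and step 4 treats the whole deficit as bias although the regression is multivariable and baseline covariates might explain part of it. Where the deficit cannot be predicted from observed scores, the mixed model and imputation would be biased too.

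The defence does not remove what the protocol itself fixes: an undefined trigger, two unordered remedies for the same failure, a replacement that discards relevant data, and an incomplete imputation rule.

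**Conclusion.** The point holds as a badly fixed rule that should be changed; it does not show that the primary result is invalid. Section 10.1 sets a loosely worded, data-dependent switch to an analysis that does not cure non-normal residuals and uses less of the data. The imputation rules in 10.1 and 10.2 need reconciling, most directly for the continuous secondary outcomes.

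On size, the choice between tests moves 2.5% to about 2.8-3.2%. The figures of 0.5-1.0 points and about 8-19% are illustrations of an unimputed fallback under one-arm informative loss. They require the mixed model to be abandoned, missingness to stay at or below 10%, and no imputation to be done. Only the part of that bias predictable from observed scores would be avoided by the mixed model or by imputation.

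**What to change.** In section 10.1, carried into the SAP:

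- Keep the mixed model as the primary analysis. Allow only non-convergence as a trigger, leading to a prespecified, ordered step-down to simpler mixed models. Non-normal residuals then fall under one rule instead of two.
- Keep the 24-month regression as a sensitivity analysis that never replaces the primary.
- Delete the 10% threshold. Always impute for that regression, with arm, the model covariates and the 5, 8 and 12 month scores in the imputation model. Without those scores, imputation would not recover what the mixed model uses.
- In section 10.2, state which analyses its imputation sentence covers, so that one rule applies to each endpoint.

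The particular step-down order is for the trial team to choose; it matters that it is fixed beforehand. The cost is wording and slightly more analysis work. Sample size, visits and data collection are unaffected.

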## **10.2 Secondary study parameter(s)**

The analysis for continuous secondary outcomes follow the analysis strategy of the primary outcome. Binary, secondary outcomes will be compared using logistic multi-level regression analysis. The stratification factors for randomization (center and gender) will be used as (fixed) covariates in the analysis and the analysis will be adjusted by a limited number of a priori defined prognostic factors (e.g. baseline WOMAC total score, age, BMI, and severity of joint damage). Relative Risks (RR) with 95% confidence intervals will be estimated.

The upper limit (lower limit for response outcomes) of the confidence interval will be compared to the respective pre-defined non-inferiority limits to determine 'non-inferiority'. An ITT and a PP analysis will be performed.

The number of complications will be reported as the frequency and percentage of events and frequency and percentage of patients experiencing events per (type of) complication. Additional arthroplasty procedures, specifically a primary knee prosthesis after KJD and revision surgery (e.g. total after hemi prosthesis) after a primary knee prosthesis will be described per group.

Radiographic assessment of joint space width, as an indicator of cartilage repair, over a two-year period will be reported descriptively in the KJD group. Differences from baseline (pre-treatment) will be tested with paired t-tests or Wilcoxon rank sum tests depending on the distribution of the data at 1 and 2 years follow-up.

Missing data will be minimised using centralised data acquisition for all participating centers coordinated from the UMC Utrecht with appropriate monitoring on data queries and will be imputed using multiple imputation by chained equations for the analyses.

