### 8.3 Study procedures

The following study assessments will be performed according to the schedule below.  
See appendices B-P for questionnaires.

	Screening/ Baseline	Pre- surg ery	Surg	Post-surgery								ET
				3w	6w	2m	5 m	8 m	12 m	24 m		
Weeks/ months	-2m (max)		0	+/- 1w	+/- 1w	+/- 2w	+/- 1m	+/- 1m	+/- 1m	+/- 2m		
Visits	V0			v1		v2	v3	v4	v5	v6		
General												
Informed consent	x											
In- and exclusion criteria	x											
Demographics/ characteristics	x											
Surgical medical history index knee	x											
Randomization		x										
Surgical treatment												
Knee prosthesis (KP) or Knee Joint Distraction (KJD) frame placement			x									
Removal KJD frame					x							
Questionnaires												
Pain Detect (neuropathic pain)	x											
KOOS (incl. pain medication)	x						x	x	x	x		
SF36	x								x	x		
EQ5D-5L	x			x		x	x	x	x	x		
NRS-Pain	x			x		x	x	x	x	x		
Patient Acceptable Symptom State	x						x		x	x		
NRS-Patient satisfaction							x		x	x		
Medical Consumption Quest. (MCQ)	x					x	x		x	x		
Productivity Cost Quest. (PCQ)	x					x	x		x	x		
Other												
Radiographic Joint space width (follow-up for KJD only) in mm **	x								x	x		
Adverse events/ additional surgical procedures *				x	x	x	x	x	x	x		
Knee flexion*	x			x	x	x	x	x	x	x		
Phone call											x	
GODIVA-bone substudy#												
Informed consent substudy	x											
In- and exclusion criteria substudy	x											
Image and biochemical markers for bone ##		x								x		

\* Adverse events / additional surgical procedures and knee flexion are specifically registered during regular care visits in a standardized way (continuous registration) so no study specific visits are planned for these measurements. Knee flexion is also measured at the baseline visit

\*\* Radiographs of the knee (according to KIDA protocol) for follow-up will only be taken after KJD (baseline X-ray for both KJD and KP). Only the 24-month x-ray is extra compared to KJD treatment in regular care according to preliminary NOV recommendations. Visits depicted in bold are study-specific clinic visits.

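### Read literally, Sections 10.1 and 10.2 adjust continuous secondary outcomes for baseline WOMAC total and not for their own baseline, which is already collected; that reading costs precision and one sentence would close it

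*Protocol*

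**What the plan says.** Two sentences in Protocol Section 10.2 bear on the adjustment of secondary outcomes.

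- Continuous outcomes: "The analysis for continuous secondary outcomes follow the analysis strategy of the primary outcome". That strategy, in Section 10.1, adjusts for "a limited number of a priori defined prognostic factors (i.e. baseline WOMAC total score, age, BMI, and severity of cartilage damage", together with centre and gender. Section 10.1 adds: "Baseline WOMAC score will be used as a continuous covariate (similar to the outcome variable".
- Binary outcomes: "Binary, secondary outcomes will be compared using logistic multi-level regression analysis". The covariate sentence comes next. After centre and gender, it says the analysis is "adjusted by a limited number of a priori defined prognostic factors (e.g. baseline WOMAC total score, age, BMI, and severity of joint damage".

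The list in Section 10.1 is closed (*i.e.*); the one in Section 10.2 is open (*e.g.*). Baseline WOMAC total is the only baseline score named in either.

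The schedule in Section 8.3 marks KOOS, SF-36, EQ-5D-5L, NRS-pain and "Patient Acceptable Symptom State" (PASS) at screening/baseline. NRS-satisfaction has no baseline mark. WOMAC scores are derived from the KOOS questionnaire (Section 8.1.1), so WOMAC subscores also have a baseline.

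Section 10.1 defers detail to a SAP, which is not shown: "All analyses and patient populations will be predefined in this SAP".

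**The concern.** In the primary model, baseline WOMAC total is the baseline of the outcome being analysed. For the SF-36 components, EQ-5D-5L, NRS-pain and the KOOS domains it is a different variable. A statistician who carries the listed covariates over unchanged would adjust the SF-36 mental component, for example, for a knee-symptom score and leave out the baseline mental component that the trial has measured.

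Section 2 makes non-inferiority on secondary patient-reported outcomes an objective, and Section 10.2 judges it by setting a confidence limit against a margin. Interval width therefore enters each conclusion directly. A less informative baseline covariate widens the interval and leaves most of any chance imbalance in the outcome's own baseline unadjusted.

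**Working it through.** **The plan's own figure.** The protocol states no precision or power for any secondary outcome. The nearest figure is 527 per arm for the primary endpoint (Section 4.4: margin 15, true difference 12, SD 15, one-sided 2.5%, power 90%):

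n = 2 × 15² × (1.960 + 1.282)² / (15 − 12)² ≈ 526 per arm by the normal approximation, and 527 with the noncentral t distribution. The figure reproduces. No covariate correlation enters it, so it is unaffected by this point.

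**Inputs for the comparison.** All correlations are assumptions, because the documents give none:

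- r = correlation of the outcome at follow-up with its own baseline: 0.3, 0.5, 0.7.
- c = correlation of baseline WOMAC total with that own baseline: 0.3, 0.5, 0.7, 0.9.
- Baseline WOMAC total informs the outcome only through the own baseline, so its correlation with the outcome is r × c. This simplification favours own-baseline adjustment.

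**Formula.** With adjustment for one baseline variable at a single time point, residual variance is 1 − r² (own baseline) or 1 − (rc)² (WOMAC total). The ratio of standard errors, own baseline over WOMAC total, is √[(1 − r²) / (1 − (rc)²)].

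| c | r = 0.3 | r = 0.5 | r = 0.7 |
|---|---|---|---|
| 0.9 | 0.991 | 0.970 | 0.920 |
| 0.7 | 0.976 | 0.925 | 0.819 |
| 0.5 | 0.965 | 0.894 | 0.762 |
| 0.3 | 0.958 | 0.876 | 0.730 |

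Two cells written out:

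- c = 0.9, r = 0.5 (a score close to WOMAC total): √(0.75 / 0.7975) = 0.970, a 3% lower standard error.
- c = 0.3, r = 0.5 (a remote score): √(0.75 / 0.9775) = 0.876, about 12% lower.

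**Range.** The reduction in standard error runs from about 1% (c = 0.9, r = 0.3) to 27% (c = 0.3, r = 0.7). As a reduction in the sample size needed for equal precision, 1 − (1 − r²)/(1 − (rc)²), it runs from 1.8% to 46.6%; at r = 0.5 it is 6.0% to 23.3%.

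**Interval width.** The 95% half-width in SD units at 527 per arm is 1.96 × √[(2/527) × residual variance]. At r = 0.5 it is 0.105 with the own baseline, against 0.108 (c = 0.9) to 0.119 (c = 0.3) with WOMAC total.

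**Limits.** This is a single-time-point linear calculation that ignores the other covariates and the repeated measures. It does not carry over to PASS: in a logistic model, adjustment does not simply shrink the standard error of the conditional odds ratio.

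**The case against.** The strongest reply is that the plan may already mean what is asked for. The covariate sentence in Section 10.2 follows the one on binary outcomes, and its list is only illustrative, so it neither fixes WOMAC total nor rules out other baselines. Continuous outcomes follow the primary strategy, and that strategy adjusts an outcome for its own baseline; carried over in that sense, it gives the SF-36 its own baseline. Covariates per outcome are also ordinarily settled in a SAP.

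Much of this stands. A reader might infer that the protocol commits every secondary comparison to the wrong baseline and so loses precision throughout. The text allows that reading but does not require it. It does not exclude it either: the inherited list in Section 10.1 is closed, and the remark there that baseline WOMAC is treated like the outcome variable may mean only that both are continuous. A SAP author could follow either reading in good faith.

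A reader might also apply one gain to all outcomes. Assuming an own-baseline correlation of 0.5 and a correlation of 0.1 to 0.3 between baseline WOMAC total and the outcome gives intervals 9% to 13% narrower, but those values suit only a remote score. KOOS pain and daily-living scores share items with WOMAC and should track it closely, so their gain is likely to be near the small end.

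Two further extensions fail. For PASS, patients enter with persistent refractory pain (Section 4.2), so baseline PASS may be negative for most and tell little; replacing the continuous WOMAC score with it could lose information. For reinterventions, Section 10.2 plans only a description per group, so there is no adjusted model to correct.

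**Conclusion.** The point holds as an ambiguity whose literal reading is inefficient. The protocol names one baseline score for adjustment, never names a secondary outcome's own baseline, and collects those baselines anyway.

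If the literal reading is followed, the standard error for a continuous secondary outcome is larger than it need be. Own-baseline adjustment would lower it by about 1% to 27% over the assumed grid: about 3% for a score close to WOMAC total (c = 0.9, r = 0.5), and more for remote scores such as the SF-36 mental component. These sizes rest wholly on assumed correlations.

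Randomisation protects against systematic bias under either reading. The primary endpoint, its margin and its sample size are unaffected.

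**What to change.** State in Section 10.2 that each continuous secondary outcome measured at baseline (WOMAC subscores, KOOS domains, SF-36 components, EQ-5D-5L, NRS-pain) is adjusted for its own baseline value, together with centre, gender, age, BMI and joint damage. Replace the illustrative list with a closed one.

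For PASS, keep baseline WOMAC total and, optionally, add baseline PASS. For NRS-satisfaction, which has no baseline measurement, use baseline WOMAC total. Leave reinterventions as they are.

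The cost is one or two sentences in the protocol, carried into the SAP before the data are analysed. No new data, visits or patients are needed.

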### Secondary Objective(s):

- To determine whether KJD is non-inferior to usual care (KP) on patient reported effectiveness regarding secondary patient reported outcomes (e.g. WOMAC subscores for pain, disabilities and stiffness, quality of life) over 2 years.
- For KJD only: To determine the change in radiographic joint space width over 2 years compared to baseline (i.e. before KJD treatment) as a surrogate marker for cartilage tissue repair.
- To describe and compare adverse events between KJD and KP (including reoperations) over 2 years.
- In the **GODIVA-bone substudy**: to predict the beneficial effects of knee distraction treatment for patients with knee osteoarthritis, based on peri-articular bone characteristics.
- In the **GODIVA-bone substudy**: to elucidate the relationship between periarticular bone changes (pre- and 2 years post-treatment) and improvement in pain perception and cartilage repair.

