5. The clinical checks after surgery will be performed in line with local clinical practice. According to regular practice, patients treated with Knee prosthesis will visit the orthopaedic surgeon at ~6 and ~12 months after surgery for a clinical check. Patients treated with Knee Joint Distraction will visit the orthopaedic surgeon after ~3 weeks for a clinical check, at 6 weeks for removal of the distraction frame, and at ~6 months and at ~12 months after surgery for a clinical check. Although the clinic visits for check-up are not part of the study visits and follow regular care practice at the local center (and thus are not specifically depicted in above scheme), data on adverse events occurring will be specifically collected during the regular care visits in a standardized way (continuous registration, via standard notation in electronic health records and entered in Castor via EHR review). This is also the case for the standard measurement of knee flexion. Questionnaires will be sent to all participants via email (via Castor EDC) at 3 weeks and at 2, 5, 8, 12 and 24 months after surgery/start distraction period). At 12 and 24 months after surgery, only patients treated with joint distraction will be invited to come to the hospital for a radiograph of the knee (after 12 months is part of regular care according to NOV recommendations). At 24 months all patients will be contacted and asked if any additional surgical procedures of the knee have been performed or planned, which will be noted.

6. In case of early study termination, a phone call will be made to ask for the reason of termination and ask if any additional surgical procedures of the knee have been performed or planned.

**For the GODIVA-bone substudy:** Standard(ised) knee-MRI (single clinical time slot comprising 3 sequences), standard(ised) knee-CT, standard(ised) DEXA (according to the Imaging manual of the substudy), vena puncture for 2 times 7 cc blood and a urine sample will be collected at baseline and 2 years after treatment. Imaging and sampling will be performed as much as possible during the visits of the GODIVA study. Only for a limited number of patients extra visits may be needed.

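### The fallback test for change in joint space width is named as the Wilcoxon rank sum test, but the data are paired and need the signed-rank test

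*Protocol*

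**What the plan says.** Section 2 of the protocol sets this secondary objective: "For KJD only: To determine the change in radiographic joint space width over 2 years compared to baseline". Section 10.2 gives the analysis. Joint space width "over a two-year period will be reported descriptively in the KJD group", and a test is then added: "Differences from baseline (pre-treatment) will be tested", where the method, for both 1 and 2 years, is described as follows: "will be tested with paired t-tests or Wilcoxon rank sum tests depending on the distribution of the data".

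Section 8.3 shows which films exist. The footnote to the schedule says that radiographs "for follow-up will only be taken after KJD (baseline X-ray for both KJD and KP"), and item 5 of the same section says that at 12 and 24 months "only patients treated with joint distraction will be invited to come to the hospital for a radiograph of the knee". Section 8.1.2 likewise restricts the endpoint to KJD.

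**The concern.** The two tests in the sentence answer different questions. The paired t-test works on one set of within-patient differences. The Wilcoxon rank sum (Mann-Whitney) test works on two independent groups and takes its null variance from that independence. The non-parametric partner of the paired t-test is the Wilcoxon signed-rank test.

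If an analyst followed the text and the data were judged non-normal, baseline and follow-up values from the same knees would be treated as two unrelated groups. Under positive correlation the p-value would be too large, and a small real change in the trial's surrogate for cartilage repair could be reported as not significant.

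**Working it through.** **1. Is there a second group?** The objective, the endpoint list and the analysis text all restrict joint space width to KJD. The schedule footnote gives KP patients a baseline film only. Each analysed knee therefore supplies a baseline value and a follow-up value, and there is no independent comparator. A rank sum test could be run only by treating the two time points as separate groups.

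**2. Number of pairs.** The protocol gives no sample size or power for this test. The only design figure is the primary one in section 4.4: margin 15, assumed difference 12, SD 15, one-sided 2.5%, power 90%.

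- Normal approximation: n = 2(1.960 + 1.282)² × 15² / (15 − 12)² = 2 × 10.51 × 225 / 9 ≈ 525.4, so 526 per arm.
- With the noncentral t distribution the result is 527, which reproduces the stated figure.

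The plan raises 527 to 600 per arm, an allowance of 73/600 = 12.2%. I take 527 as the number of KJD pairs.

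**3. False-positive rate of the test as named (approximation).** With paired bivariate normal data, the true variance of the rank sum statistic is about (1 − ρ_s) times the variance the test assumes. Here ρ_s = (6/π) arcsin(ρ/2) is the rank correlation between baseline and follow-up. The actual two-sided level is therefore about 2[1 − Φ(1.96/√(1 − ρ_s))]. The protocol does not give ρ, so it is an assumption.

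- ρ = 0.3: ρ_s = 0.288; 1.96/√0.712 = 2.32; level 2.0%
- ρ = 0.5: ρ_s = 0.483; 1.96/√0.517 = 2.72; level 0.64%
- ρ = 0.7: ρ_s = 0.683; 1.96/√0.317 = 3.48; level 0.05%

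**4. Simulation, normal data, 527 pairs, two-sided 5%, 3,000 runs per setting.** Correlation and shift are assumed. The shift is in units of the between-patient SD at one time point.

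| ρ | No change: rank sum | No change: signed-rank | Shift 0.10 SD: rank sum | Shift 0.10 SD: signed-rank |
|---|---|---|---|---|
| 0 | 5.0% | 5.0% | 37% | 37% |
| 0.3 | 1.9% | 4.8% | 32% | 46% |
| 0.5 | 0.6% | 4.3% | 30% | 60% |
| 0.7 | 0.07% | 6.0% | 25% | 83% |
| 0.9 | 0% | 4.5% | 12.5% | 99.9% |

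The simulation error at a 5% level is √(0.05 × 0.95/3000) = 0.4 percentage points. The two tests agree at ρ = 0, so the loss comes entirely from ignoring the pairing.

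**5. Larger shifts and skewed data, ρ from 0.5 to 0.9.** These runs used 510 pairs (500 in the last row), slightly fewer than 527. The difference is immaterial.

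| Data | Shift | Rank sum power | Signed-rank power |
|---|---|---|---|
| Normal | 0.15 SD | 71–87% | 90–100% |
| Normal | 0.20 SD | 94–100% | 99–100% |
| Lognormal, sigma 0.5 | 0.10 SD | 51–56% | 76–100% |
| Lognormal, sigma 0.5 | 0.15 SD | 92–99.9% | 97–100% |
| Lognormal, sigma 0.5 | 0.20 SD | 99.6–100% | 99.7–100% |
| Lognormal, sigma 0.8 | 0.10 SD | 92–99.9% | 94–100% |

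With no change, the rank sum test rejected in 0 to 0.65% of the lognormal (sigma 0.5) runs.

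**The case against.** The intent is clear. The sentence speaks of differences from baseline and names a paired t-test first, so a competent analyst would probably run the signed-rank test anyway, and the SAP is a natural place to correct the name. The stakes are low: this is the fallback of a within-arm secondary test with no non-inferiority decision attached, on an endpoint that is mainly reported descriptively. With several hundred pairs the paired t-test is robust. In the lognormal (sigma 0.5) setting it rejected in 4.8 to 5.1% of runs without change, so the fallback may never be needed. A conservative test also still controls the false-positive rate.

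All of this stands as a limit on importance. Two cautions also stand. First, the conservatism depends on positive correlation, which is plausible for the same knee but not stated in the protocol. Second, the protocol gives no rule for choosing the fallback, so the skewed cases only illustrate when it might be used. With equal skew at both times and a constant shift, the differences themselves are roughly symmetric and heavy-tailed.

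None of this makes the named test right. The protocol is not silent on the point: it specifies a test that does not fit its own data. A SAP that followed it would repeat the error, and a SAP that corrected it would depart from the protocol.

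**Conclusion.** The concern holds and is minor. The wrong test is named for paired, single-arm data, and nothing else in the protocol supplies an independent group that would justify it. Under positive correlation the consequence is a miscalibrated, conservative p-value. The loss of power is large only for small shifts (about 0.10 SD, and 0.15 SD in normal data) and is slight or nil from 0.20 SD. These sizes rest on assumed correlations, shifts and distributions. Under positive correlation the error cannot create a false claim of cartilage repair.

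**What to change.** In section 10.2, replace the rank sum test with Wilcoxon signed-rank tests on within-patient differences, and use the same name in the SAP. This changes one term and needs no change to sample size, data collection or visits.
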